9.0 Data and Safety Monitoring Plan

This section is required when research involves more than Minimal Risk to subjects as defined in “HRP-001 SOP- Definitions.”

Minimal Risk is defined as the probability and magnitude of harm or discomfort anticipated in the research that are not greater in and of themselves than those ordinarily encountered in daily life or during the performance of routine physical or psychological examinations or tests. For research involving prisoners, Minimal Risk is the probability and magnitude of physical or psychological harm that is normally encountered in the daily lives, or in the routine medical, dental, or psychological examination of healthy persons.

Please complete the sections below if the research involves more than minimal risk to subjects, otherwise indicate each section as not applicable.

[Do not type here]

9.1 Periodic evaluation of data

Describe the plan to periodically evaluate the data collected regarding both harms and benefits to determine whether subjects remain safe.

Growth charts will be reviewed in real time at patient visits. Those meeting criteria for growth failure (failure-to-thrive) described above will be immediately flagged and discussed with [name].

9.2 Data that are reviewed

Describe the data that are reviewed, including safety data, untoward events, and efficacy data.

For this 6 month trial, growth charts are the data that will be reviewed.

9.3 Method of collection of safety information

Describe the method by which the safety information will be collected (e.g., with case report forms, at study visits, by telephone calls and with subjects).

Any growth failure event will be considered an adverse event, and these will be captured with a case report form.

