3.1 Inclusion Criteria

Create a numbered list of the inclusion criteria that define who will be included in your final study sample (e.g., age, gender, condition, etc.)

1. Term or Early Term (≥ 37 weeks), singleton infants
2. Infant birthweight $\geq 50^{\text{th}}$ percentile based on the 2013 Fenton Growth Charts (which account for sex of child and gestational age at birth)
3. Infant without substantial neonatal morbidity that would affect feeding or weight gain (e.g. known chromosomal abnormality, metabolic disorder, cleft lip/palate, etc.)
4. Infant age ≤ 1 month
5. Mothers with pre-pregnancy body mass index $\geq 25 \text{ kg/m}^2$
6. Mothers ≥ 18 years old
7. Parental plan to exclusively feed infant 19-20 kcal/ounce formula upon delivery or by the start of the intervention period ~ 1 month after delivery
8. Parental intention to have infant well child visits through age 6 months at a Division of Academic General Pediatrics practice site (Hope Drive, Elizabethtown, Nyes Road)
9. English speaking parent

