7.1 Study Design

Describe and explain the study design.

This study is a randomized, clinical trial involving 60 exclusively formula fed infants born at ≥ 37 weeks gestational age who are at-risk for overweight based upon maternal pre-pregnancy overweight or obesity (or alternatively at first prenatal visit if pre-pregnancy weight/height not known) and infant birthweight $\geq 50^{\text{th}}$ percentile. Infants will be enrolled at Penn State Health Children's Hospital or at affiliated clinics within the Division of Academic General Pediatrics between birth and age 1 month, where they will be randomized to a calibrated formula intake intervention or control. Participating infants in the intervention group will be seen monthly until age 6 months where they will be weighed and measured, and parents will complete surveys related to volume of formula consumed, infant appetite, parent feeding style, and infant temperament. Control infants will follow the same procedures, but will not have scheduled visits at ages 3 and 5 months. Instead their visits will correspond to usual care well child visits at ages 1, 2, 4, and 6 months.

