9.4 Frequency of data collection

Describe the frequency of data collection, including when safety data collection starts.

Data are collected per the visit schedules for the intervention and control groups.

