9.7 Statistical tests

Describe the statistical tests for analyzing the safety data to determine whether harms are occurring.

As we expect adverse events to be infrequent, we are not planning to do any interim safety analyses.

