10.0 Risks

List the reasonably foreseeable risks, discomforts, hazards, or inconveniences to the subjects related to the subjects' participation in the research. Include as may be useful for the IRB's consideration, a description of the probability, magnitude, duration and reversibility of the risks. Consider all types of risk including physical, psychological, social, legal, and economic risks. Note: Loss of confidentiality is a potential risk when conducting human subject research.

- If applicable, indicate which procedures may have risks to the subjects that are currently unforeseeable.
- If applicable, indicate which procedures may have risks to an embryo or fetus should the subject be or become pregnant.
- If applicable, describe risks to others who are not subjects.

It is possible that a reduction in formula intake could lead to temporary growth faltering (i.e. failure-to-thrive), though this would be self-limited and could be addressed by subsequently increasing formula intake.

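### Harms other than growth failure are not systematically collected by arm, so the pilot could make no between-arm statement about them

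*Combined protocol and SAP*

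**What the plan says.** Section 9.2 states the scope of review: "For this 6 month trial, growth charts are the data that will be reviewed". Section 9.3 then names the one event that goes on a form: "Any growth failure event will be considered an adverse event, and these will be captured with a case report form". On timing, section 9.4 says "Data are collected per the visit schedules for the intervention and control groups", and those schedules differ: "Control infants will follow the same procedures, but will not have scheduled visits at ages 3 and 5 months" (section 7.1). Section 9.7 adds "As we expect adverse events to be infrequent, we are not planning to do any interim safety analyses". In section 9.8 the only suspension trigger based on harm is failure-to-thrive in more than 33% of the intervention group.

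This follows the risk section, which foresees one harm: "It is possible that a reduction in formula intake could lead to temporary growth faltering (i.e. failure-to-thrive" (section 10.0). Section 7.2.2 also argues the safety of the 10% step in terms of failure-to-thrive.

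Two other provisions matter. Section 18.1 sends a harm to the IRB if it has been observed or reported and the investigator judges it unexpected and probably related. Section 3.3.2 ends all data collection once an infant is withdrawn.

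**The concern.** The intervention lowers the advised feeding volume for some infants from about one month of age. Growth is measured about monthly in the intervention arm, and at 1, 2, 4 and 6 months in controls. An acute illness, emergency visit or admission that resolves between two weighings may leave no mark on the growth chart, and the plan has no other place where it would be written down.

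What is at stake is the information the pilot leaves behind. Section 8.2 says its data will be used to size a full trial, and section 11.2 says it could inform feeding guidelines. A report with no non-growth events listed could not show whether none occurred or none were recorded.

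**Working it through.** The plan gives no figure to reproduce; the sample size of 60 rests on feasibility (section 8.2). The check sets the sections side by side, then puts a scale on what collection could show.

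**Step 1. Is there any route by which a non-growth harm enters the study data?**

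| Place | What is collected | Non-growth harm? |
|---|---|---|
| 7.2.1 to 7.2.7 | Weight, length, intake diaries, feeding and temperament surveys | Not asked |
| 4.2.4, 7.2.1 | Record review for eligibility, pregnancy and birth history | No later abstraction described |
| 9.2, 9.3 | Growth charts; growth failure on a form | No |
| 1.3, 8.3 | Endpoints and analyses | No safety endpoint, no adverse event summary by arm |
| 18.1 | Harms observed or reported, then filtered | Possible, but with no question, form, schedule or count by arm |

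Only 18.1 reaches beyond growth, and it is passive.

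**Step 2. Who is advised a reduced volume?** Under 7.2.2, intervention infants below the 75th weight-for-length percentile are advised the calculated requirement with no reduction. Those at or above it are advised 10% less, and under 7.2.3 15% less if they are there for a second consecutive month. The reduced-volume group is thus a subset of the intervention arm, and the protocol does not state its expected size.

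**Step 3. Would spontaneous reports be comparable?** From month 1 the intervention arm has 6 scheduled visits (1, 2, 3, 4, 5, 6 months) and the control arm 4 (1, 2, 4, 6 months). Events after Visit 2 could be mentioned at 6 − 1 = 5 later visits in one arm and 4 − 1 = 3 in the other. Unprompted reports would therefore not be comparable, even if every one were noted.

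**Step 4. What could complete collection show?** With zero events in n infants, the one-sided 95% upper limit is 1 − 0.05^(1/n). The allocation ratio is not stated, so 1:1 (30 per arm) is an assumption.

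- n = 30 (whole intervention arm): 1 − 0.05^(1/30) = 9.5%.
- n = 20 (one-third attrition, assumed): 1 − 0.05^(1/20) = 13.9%.
- n = 15 (half the arm advised a reduced volume, assumed): 1 − 0.05^(1/15) = 18.1%.

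The chance of seeing at least one event is 1 − (1 − p)^n:

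| True rate p | n = 30 | n = 15 |
|---|---|---|
| 1% | 26% | 14% |
| 2% | 45% | 26% |
| 5% | 79% | 54% |
| 10% | 96% | 79% |

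Without collection there is no numerator, so none of these statements can be made.

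**The case against.** A fair defence is that the monitoring follows the risk. Growth faltering is the harm the protocol foresees; it is measured directly, charts are reviewed in real time and cases are flagged at once (section 9.1). Infants stay under their own pediatricians (section 15.4), and other harms have the route in 18.1. Intake diaries and an eating-behaviour questionnaire are used in both arms, and the content of parent forms is kept out of the protocol by its template (section 7.0). Events are expected to be rare and the trial is small.

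Part of this stands. Growth failure is looked for, and rarity is a reasonable ground for having no interim safety test. But section 9.7 speaks to interim analysis, not to whether events are recorded. Usual care may treat an event without passing it to the study. The named surveys concern feeding and temperament and are not safety instruments.

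Three stronger readings are tempting, and the documents do not support them:

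- A reader might infer that the pilot will call the intervention safe without having looked. Sections 1.2, 1.3 and 8.3 plan no safety endpoint or conclusion; section 11.2 is a hedged line on benefit to others. Growth is looked at throughout.
- A reader might infer that every intervention infant is on a reduced volume. Step 2 shows that this is a subset, and 7.2.2 also tells parents to prepare more formula if hunger cues persist.
- A reader might take 9.5% as the size of the defect. It is computed on the whole arm and describes the limits of a 60-infant pilot.

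**Conclusion.** The gap is real but bounded. As written, harms other than growth failure are not systematically collected, and any that surface would do so through a filtered route with unequal opportunity by arm. The pilot could make no between-arm statement on them. It is not a claim that the intervention is unsafe.

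The change is worth making because it is cheap and alters no feeding rule, but its yield should not be oversold. Zero events would leave rates up to 9.5% compatible with the data for a whole arm of 30, and up to 18.1% for a subgroup of 15. These limits rest on 1:1 allocation, complete follow-up and, for the subgroup, an assumed half of the arm; the protocol states none of the three.

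**What to change.** In sections 9.2 and 9.3, provide that:

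- Existing coordinators record from the medical record all unscheduled, emergency and inpatient encounters and feeding- or hydration-related diagnoses, on one form in both arms and over the same window (Visit 2 to age 6 months). Enrolment requires "Parental intention to have infant well child visits through age 6 months at a Division of Academic General Pediatrics practice site" (section 3.1), which makes this practicable for care within the system.
- One standard question on acute care since the last shared visit is put to parents in both arms at 2, 4 and 6 months. The 3- and 5-month visits are not used, so that the opportunity to report is equal.
- Counts with exact intervals are reported by arm, and descriptively for infants who were advised a reduced volume.

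Section 3.3.2 has to be amended too, because it now stops all data at withdrawal, including withdrawal for failure-to-thrive. Let this record abstraction continue after study-initiated withdrawal (failure-to-thrive or missed visits) where consent and authorization allow. Otherwise, report events up to withdrawal with the follow-up time in each arm.

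Cost: one short form, a few minutes per infant for 60 infants, and a check that consent and authorization cover later abstraction (the consent form is not in the document reviewed). Care outside the system would be caught only by the parent question, and the intervals will be wide.

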9.4 Frequency of data collection

Describe the frequency of data collection, including when safety data collection starts.

Data are collected per the visit schedules for the intervention and control groups.

9.5 Individuals reviewing the data

Identify the individuals who will review the data. The plan might include establishing a data and safety monitoring committee and a plan for reporting data monitoring committee findings to the IRB and the sponsor.

The study coordinators and PI will be the ones reviewing the data.

9.6 Frequency of review of cumulative data

Describe the frequency or periodicity of review of cumulative data.

Cumulative data will be reviewed at the end of the trial.

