3.3 Early Withdrawal of Subjects

3.3.1 Criteria for removal from study

Insert subject withdrawal criteria (e.g., safety reasons, failure of subject to adhere to protocol requirements, subject consent withdrawal, disease progression, etc.).

1. Infants exhibiting failure-to-thrive defined as:
 - a. Weight-for-length $< 5^{\text{th}}$ percentile for sex and age on the WHO growth chart
 - b. Downward crossing of > 2 major centile lines on the WHO growth chart (relevant major lines include 95th, 90th, 75th, 50th, 25th, 10th, 5th) after enrollment
2. Non-adherence to the study visit schedule characterized by failing to complete **two** scheduled study intervention visits within 2 weeks of turning 1, 2, 3, 4, and 5 months old (does not include enrollment and final visit)

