9.8 Suspension of research

Describe any conditions that trigger an immediate suspension of research.

Suspension of the research would occur if:

1. >33% of participants are not adhering to the data collection procedures
2. >33% of intervention group participants meet criteria for failure-to-thrive
3. Attrition exceeds 33% after Visit 2

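### The failure-to-thrive suspension trigger in 9.8 is a group proportion with no scheduled evaluation before the end of the trial

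*Combined protocol and SAP*

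**What the plan says.** Section 9.8 answers the template prompt "Describe any conditions that trigger an immediate suspension of research". Its second condition is ">33% of intervention group participants meet criteria for failure-to-thrive". The other two conditions, on adherence to data collection and on attrition, also use 33%.

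Section 9.6, which sets how often cumulative data are looked at, says in full: "Cumulative data will be reviewed at the end of the trial". Section 9.7 adds: "As we expect adverse events to be infrequent, we are not planning to do any interim safety analyses".

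For the individual infant the plan is more active:

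- Under 9.1, growth charts are reviewed at each visit, and infants meeting the criteria "described above will be immediately flagged and discussed with" a named individual.
- Section 9.3: "Any growth failure event will be considered an adverse event, and these will be captured with a case report form".
- Section 9.5: "The study coordinators and PI will be the ones reviewing the data".
- Section 3.3.1 makes failure-to-thrive a ground for removal from the study. Section 3.3.2 collects no further data after removal and does not replace the infant.
- Sections 7.2.2 and 7.2.3 limit the volume reduction to infants at or above the 75th weight-for-length percentile: 10%, rising to 15% after a second consecutive month. Volumes are recalculated at each monthly visit.

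Section 15.5 provides for team meetings at least once a month, under the heading of informing the study team and with no safety item listed.

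**The concern.** No single visit can show that more than a third of the arm has met failure-to-thrive. Somebody has to add up cases, divide by a stated denominator and compare the result with 33%. The plan does not say who does this, when, or over which denominator. The only date it gives for looking at accumulated data falls after every infant has finished. A rule meant to act immediately is therefore paired with a review schedule that, followed literally, first tests it when there is nothing left to suspend.

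Withdrawal protects the infant already affected. Trigger 2 is the plan's one numerical rule for asking whether the feeding recommendations should go on for the rest of the arm. Section 10.0 names growth faltering as the foreseeable risk, section 2.2 reports no preliminary data, and no monitoring committee is named. The low event rate in 9.7 is thus an expectation, and trigger 2 is the safeguard if that expectation is wrong.

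**Working it through.** **Reading the sections together.** The 33% threshold is stated without a derivation, so there is no figure to reproduce. The provisions that bear on a count are:

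| Section | What it provides | Group count? |
|---|---|---|
| 3.3.1, 3.3.2 | removal of the affected infant | no |
| 9.1, 9.3 | real-time flag; case report form | no, case by case |
| 9.4, 9.5 | collection by visit; names the reviewers | no timing of a count |
| 9.6 | cumulative review | end of trial only |
| 9.7 | interim safety analyses | none |
| 15.5 | meetings at least monthly | not on a stated agenda |
| 18.1 | reports of harms to the IRB | no, case by case |

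**Inputs for scale.** From the documents: 60 infants and a 6-month recruitment period (8.1), and 6 months' participation (7.3). Assumed: 1:1 allocation (not stated), so 30 intervention infants; even entry, 5 per month; enrolment at birth; recommendations from age 1 to 6 months. All true failure-to-thrive rates below are assumptions.

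**Timeline.** At month 2, 10 intervention infants are randomized and 5 are on recommendations. At month 7 the figures are 30 and 25. At month 11, 5 remain on recommendations, and at month 12 none. Total time on recommendations is at most 30 × 5 = 150 infant-months, all of it before the scheduled review. This covers full and reduced volumes together.

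**Cases needed.** The smallest k with k/n > 0.33 is floor(0.33n) + 1. For n = 30, 0.33 × 30 = 9.9, so k = 10. For n = 10, 15, 20 and 25, k = 4, 5, 7 and 9. For n = 3, 0.99 gives k = 1.

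**Chance that the trigger is met at full enrolment**, exact binomial P(X ≥ 10), n = 30:

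| True rate | 5% | 10% | 20% | 30% | 40% | 50% |
|---|---|---|---|---|---|---|
| Probability | 0.0000012 | 0.00045 | 0.061 | 0.411 | 0.824 | 0.979 |

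**What a monthly count would gain.** Simulation of 100,000 trials: event age uniform between 1 and 6 months, each event counted at the next monthly visit, all infants randomized to date in the denominator, withdrawn infants kept. At a 40% rate the trigger is met before month 12 in about 78% of trials. Among trials that meet it, the median is month 9, with on average about 10 infants and 18 infant-months of recommendations still ahead. If events could be counted on the day they occur, the figures would be 80%, 11 infants and 23 infant-months. Detection at visits is the fairer assumption because 9.1 works through visits. At rates of 10% or less the trigger is almost never met, so almost nothing is gained.

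**What a monthly count would cost in pauses by chance:**

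| Counting rule | 5% | 10% | 20% |
|---|---|---|---|
| Monthly looks, all randomized to date, with or without a minimum of 10 | about 0% | about 0.05% | about 6% |
| Fully followed infants only; looks at 10, 15, 20, 25, 30 | 0.14% | 2.0% | 22% |
| Fully followed infants only; look after every infant from 10 to 30 | 0.24% | 3.0% | 27% |
| Fully followed infants only; look after every infant, no minimum | 15% | 30% | 60% |

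The first row is close to the single final count (0.0001%, 0.05%, 6%), so repeated looks with that denominator add very little. The denominator, which 9.8 leaves undefined, drives the risk.

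**The case against.** The strongest reply is that the trigger will work in practice. The condition in 9.8 is worded as standing and is not tied to the 9.6 review. Every case reaches a small team at one institution as it happens, through the flag, the form and the withdrawal call. With about 30 intervention infants, that team would be unlikely to miss ten cases. On this reading 9.6 describes the formal closing review and leaves 9.8 free to operate, and 9.7 is a reasoned decision for a short feasibility pilot. Much of this stands. An informal count is likely, and that lowers the practical consequence. It still supplies no scheduled comparison with 33% and no denominator.

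A reader might infer three stronger things that the documents do not support:

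- *Infants are unmonitored until the end.* They are not: 9.1, 9.3 and 3.3.1 act on each infant at once.
- *The 150 infant-months are exposure to restricted feeding.* Only infants at or above the 75th weight-for-length percentile receive a reduction. One who falls below that line returns to the full calculated volume at the next visit, before any trial-level rule is needed.
- *The plan needs an interim hypothesis test.* A tally against a threshold already in the protocol is enough.

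The size of the benefit also rests on rates far above what the protocol expects. Section 9.7 calls adverse events infrequent, and 7.2.2 chose 10% as unlikely to cause failure-to-thrive. At a true rate of 20% the trigger is met in only about 6% of trials.

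**Conclusion.** The point holds at trial level. A rule for immediate suspension has no scheduled evaluation while infants are on feeding recommendations, because the only scheduled cumulative review comes at the end. Triggers 1 and 3 share the gap but concern trial conduct.

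The gap matters only if failure-to-thrive is far more common than expected, which is the case trigger 2 exists for. At an assumed 40%, a monthly count would bring the decision forward in about 78% of trials, with about 10 infants and 18 infant-months of recommendations still to come. At 10% or less the gain is close to nil. These figures rest on 30 intervention infants, even entry, enrolment at birth and detection at monthly visits. Section 1.1 gives randomization at 2–3 weeks after birth, which would shift the calendar slightly.

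Severity is low to moderate: individual protection is in place and no estimate changes, but a safety rule should say when it is checked.

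**What to change.** Amend 9.6 along these lines:

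> The coordinators and PI will compare the 9.8 proportions with their thresholds at each team meeting, at least monthly. For trigger 2 the denominator is all intervention infants randomized to date; withdrawn infants stay in numerator and denominator. No interim hypothesis test is planned. The final cumulative review is retained.

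Running the comparison at each new failure-to-thrive case report form would serve equally well. The 9.8 thresholds stay as they are.

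A minimum count before trigger 2 applies, for example 10 intervention infants, is optional with this denominator. It would be needed if only fully followed infants were counted, since 1 of 3 already exceeds 33%. Any minimum would be an addition to 9.8, which has none now.

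The cost is a sentence or two and a short monthly tally from forms already completed, with no extra visits or staff. The downside is the small chance of a pause by chance shown in the first row of the last table.
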